**PN Program Analytics.**

Program analytics (i.e., log data) to be collected include

total time spent accessing PN, time spent on each module and activities within modules, and number of activities and modules completed. These data will be captured through HTML5 programming and downloaded into Excel. From this data, we will be able to examine the depth of parents’ immersion in the program and distinguish between users who quickly moved through the program versus those with a deeper level of engagement as well as assess accuracy and use them to assess effects of program exposure (i.e., dose).

**Fidelity of PN Use.** We will assess fidelity in several ways. First, we will use the program analytics described above to verify access to PN. Second, we will use practices to ensure that all parents carefully read the PN at least once. We will ask parents to rate each section of the PN in terms of how readable, useful, and interesting they were. Past studies on the Parent Handbook have shown that ratings tend to be uniformly positive, with means on 4-point scales ranging from 3.07 to 3.71 (SDs ranged from .55 to .94). Third, parents will be asked if they had discussed specific topics covered in the PN using 4-point scales ranging from (1) not at all to (4) a great deal. Past studies on the Parent Handbook have shown >70% of parents report they had discussed all topics. In our past studies, we have asked parents to underline segments of the Parent Handbook that resonate for them and make comments in the margins of the materials, and found that >70% return the materials with markings and comments throughout (almost all comments being uniformly positive). In the current study, we will have an option where parents can click on an icon to add a comment on any section of the PN modules. We will encourage them to do so, letting them know that it will help us understand content they particularly like or feel needs to be refined. Based on our previous work, we anticipate >70% of the parents will read the PN thoroughly, rate the content positively, and communicate the content with their teens.

In our previous work we generally get more mothers (80%) than fathers (20%) to participate. When we have examined the response rates and backgrounds of our families in our previously funded research, we have observed no significant demographic or general attitude biases when we compared parents who agreed to participate in our studies with those who were unwilling to do so.

**Table 2. Measures Reflective of Theoretical Model in Figure 1**

Construct	Target	Time	alpha
Primary Outcomes			
Alcohol Use (Daily Drinking, HED, Quantity/Frequency, Peak) 	Teen	T1-T3	>.70-.90
Alcohol-related Consequences (e.g., Riding with a drunk driver) 	Teen	T1-T3	>.75-.85
Secondary Outcomes			
Marijuana Use 	Teen	T1-T3	>.70-.90
Nicotine Use (e.g., Cigarette Use; E-cigarette Use; Smokeless Tobacco) 	Teen	T1-T3	>.70-.90
Combined Substance Use	Teen	T1-T3	>.70
Tertiary Outcomes (Mediators)			
Parent Communication 	Parent,Teen	T2	>.75
Alcohol Motives/Expectancies/Willingness/Norms 	Teen	T2	>.70 - >.85
Moderators			
Background Demographics (Birth Sex, Gender Identity, Sexual Orientation, Age, Race / Ethnicity)	Teen	T1	–

**Participant retention and plans to increase retention.** Our retention goals are to have a final sample representative of the U.S. population, free of sample bias, and of sufficient power to address our study aims (see Attrition and Statistical Power sections below). This has been our experience in two large-scale national sample studies with GfK. As indicated, GfK's panels tend to outperform other large national panels on known and standard benchmarks (e.g., Census data). GfK's panels typically observe a 2% monthly panel attrition rate that is not-study specific, study-specific retention rates of 80% for short-term follow-ups (1-3 months) and 70% retention in longer-term follow-ups (6-12 months). In [name]'s recent national RCT study with GfK, he observed a 78% participation rate for teens similar to the proposed study and retained 88% at 12 months. Our procedures make every attempt to reduce attrition by keeping respondent contact information current and using methods we have employed in our past work. First, in the initial baseline survey, participants will list and provide contact information for two individuals they DO NOT live with whom we may contact in the event we are unable to locate participants with our contact information, as well as a cell phone number at which they can receive text message reminders. Second, at the beginning of each post-assessment, participants will be contacted by email and asked to update their own contact information and that of the two individuals they indicated as contact individuals in the previous assessment. If they do not respond, we will follow-up by phone. Finally, we will provide sufficient incentives and multiple contacts (up to 7 email reminders) that help with high retention. Using these procedures for the 400 parent-student dyads at baseline, we anticipate the 2% monthly non-study specific attrition will result in n's of 320 and 280 dyads at the 1- and 6-month follow-ups.

**Attrition analyses.** We will first examine if the attrition is random by forming a dummy variable that indicates completion or drop-out at each assessment. The dummy variable will be correlated with key variables in the study (e.g., Group, drinking outcomes). In the past, we have observed nonsignificant correlations suggesting that the attrition has been random and then used the most advanced multiple imputation techniques to impute missing data. We then analyze all cases with the imputed data. Although we have not observed differential attrition by condition, we recognize the potential. We will reduce this possibility by providing the controls with an online link to the intervention at the completion of the 6-month assessment. Thus, all conditions will be identical except for the timing of intervention. However, if we should observe non-trivial correlations (e.g.,  $> .2$ ) between the dummy variable reflecting completers vs. drop-outs, we will include the dummy coded variable as a covariate in subsequent analyses and attempt to interpret significant effects.

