KB will refine and complete the digital programming of PN in consultation with the research team. Investigators have developed goals and specific instructional/behavioral objectives and content for the PN in Phase I. During Phase II, KB will iteratively share content with all members of the team who will review and provide feedback for any remaining revisions. We used a combination of emails, telecommunications, Zoom teleconferencing, and in-person meetings in Phase I (meeting weekly and more often as needed). We will utilize this same approach in Phase II. This process will continue until all necessary improvements are made. Following completion of the digital programming for the remaining modules, we will conduct a usability study that mirrors the approach we used in Phase 1. The functionality of the PN program will be tested by KB on a small group of parents (~n = 5-7). Edits will be made based on these findings and then tested again on another small group of parents (~n = 5-7). Based on our experience on the development time in Phase I, we anticipate this process to be completed in 6 months.

**Limitations and Alternative Methods for Objective 1.** Face-to-face delivery and/or a longer curriculum may be more effective in reducing substance use. Future research should compare modalities, but the current design facilitates delivery with minimal training and increased consistency, maximizing usability with varied groups. A native mobile app could be produced but it is more expensive and can take longer to produce for multiple device operating systems, is more challenging to update, and its use cannot be as easily monitored as a web app.

**Milestones/Deliverables for Objective 1.** The benchmark for Objective 1 is when all of the above steps are accomplished and PN is revised to specifications and fully operational with a high degree of usability as expressed in SUS scores above the 68 standard.

**Objective 2: Conduct a randomized clinical trial to evaluate outcomes of the PN curriculum. Randomized Trial Design.** The design is a two-arm RCT (PN vs. active control) with 3 waves of data collection: pre-intervention baseline, short-term follow-up (1-month), and longer-term follow-up (6-month). The study will enroll a nationally representative sample of 400 parent-student dyads through GfK Custom Research (formerly known as Knowledge Networks). Youth will complete assessments of all the variables in

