### **Specific issues and approaches for the analyses of the Specific Aims.**

**Aim 1: Evaluate the efficacy of PN intervention.** The primary focus of the analyses will document differences on our primary outcomes (alcohol use and alcohol-related harms) and secondary outcomes (marijuana use, nicotine use, and their combined use with alcohol) between the groups (PN/Control) using a mixed measures analysis of variance. A 2 X 3 (groups X time) MANCOVA will test the impact of the PN intervention on our outcome variables contrasting baseline tendencies against follow-up assessments (3 waves: baseline, 1 mo., and 6 mo.). For Aim 1 (analysis of efficacy), we will conduct an intent-to-treat analysis that will include all individuals who have been randomized to a condition. We will also examine differences in all outcomes by sex of the student (as a relevant biological variable), sexual orientation, and gender identity adding these as covariates to the analyses. We will be sensitive to inflated experiment-wise error rates and control these with modified Bonferroni methods.

**Aim 2: Examine mediators.** The second aim examines mediation paths in Figure 1 using SEM. We will follow the recommendations of MacKinnon (joint significance). For example, we will examine the relationship between the effects of the PN on predictors at the immediate post-PN assessment (1 mo. follow-up) and their subsequent effects on outcomes at the 6 month follow-up. The models will be statistically over-identified. We will examine global fit indices and focused indices of fit diagnostic of specific points of ill fit in the model (e.g., standardized residuals for predicted minus observed variances and covariances, and modification indices). We will use robust standard errors and bootstrapping. In the face of poor model fit, we will examine diagnostics that are conceptually meaningful and will significantly improve model fit.

[figure not shown]

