### **Multiple Trajectories that Covary.**

The analyses can be extended to identify multiple trajectories that covary over time and by group (PN/Controls; Figure 3). For example, the analytic approach would examine the changes over time in parental communication (PCOM) associated with the changes over time in alcohol use and include the effects of time-invariant covariate of PN (vs. controls). This growth curve can be expanded to include other constructs (e.g., parent communication). The focus is on trajectories of change over time rather than single variables. These analyses have not been done in any previous research examining brief PN efficacy or mediation processes in alcohol use but have been used

in other risky behavioral areas with good effect. This also can be modified for lagged effects and complex structural dynamics typically discussed in traditional panel analysis. It is possible to parameterize a growth curve model in traditional panel analysis terms like it is possible to parameterize traditional panel analysis in growth curve model terms. The mathematical details can be rather complex, and our experience is that typical social science readers are more comfortable with one framework or the other, depending on the research question. Our point is that for questions that pursue the analysis of the relationship between multiple trajectories, fairly complex causal dynamics and error structures can be modeled.

**Limitations/Alternative Strategies for Aim 2.** An alternative would be to recruit a school district or an adequate number of schools, randomly assigning schools to condition. This would not, however, produce a nationwide sample and would be costly in recruitment and tracking. Administration under these conditions is not, however, directly analogous to eventual dissemination. We accept this tradeoff for the advantages of a representative, national sample.

**Indicators of Success/Benchmarks.** One indicator of success will be if we hit initial, 1- and 6-month recruitment and retention targets. Secondly, we expect a high degree of fidelity (i.e., 80% accessing all required material and at least one optional section). The next indicator would be short term effects on mediators on the 1-month follow up. Finally, and most importantly, will be significant effects on behavioral outcomes with a successful test of the conceptual model in Figure 1.

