## Protection of Human Subjects

### 1. Risk to the Subjects

*Human Subjects Involvement and Characteristics:* Participants recruited to the research study total 400 parent-teen dyads. The teens (aged approximately 16-17) will be current high school students.

*Inclusion criteria:* Teens who are currently in high school, along with a parent (or parental figure). Dyads will be fluent in English and have smartphone, tablet or computer Internet access. Alcohol use is not required for inclusion in the study. There are also no other exclusion criteria for recruitment other than not meeting inclusion criteria. Teens will be incentivized (amount in brackets) to individually complete a total of 3 assessments including baseline (incentive of \$10 plus \$5 bonus for early return), 1-month follow-up (\$15 plus \$5 bonus for early return), and 6-month follow-up (\$20). Parents will participate in the Parenting Now intervention or an active control intervention (\$15 incentive) and complete 1-month follow-up assessment of the intervention (\$15 incentive). Each assessment will take no longer than 25-30 minutes to complete. All assessment procedures proposed in the current study have been used in previous research without adverse incident.

*Sources of Material:* Research material will consist of self-report responses to web surveys. At baseline, all youth will be asked about alcohol, marijuana, and nicotine use, combined substance use, willingness to use alcohol, alcohol motives, alcohol expectancies, norms about alcohol use, parenting behaviors and basic demographics. Parents will be asked to rate their perceptions of the interventions (interest, usability, etc.). All measures will be completed confidentially and will be collected only for research purposes. Data will not be shared between parents and teens.

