For Aim 2, we will use structural equation modeling (SEM) to assess paths between the Group (PN vs. Control) and the mediators (parent-child communication, parental monitoring, parental permissiveness) and student factors at follow-ups (e.g., motives, behavioral willingness, norms, expectancies) as described in MacKinnon et al. In terms of determining the proper sample, the use of SEM means that in addition to statistical power, issues of the stability of the covariance matrix, model complexity, and use of asymptotic theory must be taken into account. In terms of power, it is difficult to evaluate the power associated with specific path coefficients in complex SEM models due to the large number of assumptions about population parameters that must be made. A rough approximation can be obtained by applying power analyses for a coefficient in multiple regression analyses in the context of limited information estimation of path models. As an example, for a regression analysis with 5 predictors (e.g., intervention group, parent discussions, student motives, behavioral willingness, sex, and age) where the squared multiple correlation is 0.25 and where one wants to detect a predictor accounting for at least 5% unique variance in the outcome (e.g., alcohol misuse or alcohol-related consequences), the sample size to achieve power of 0.80 is approximately 125. For a logistic regression analysis having a dichotomous outcome (e.g., yes/no to heavy episodic drinking in past 30 days) where the target predictor is a continuous predictor (e.g., motives), with four other predictors in the equation (e.g., group, parent discussions, sex, and age), where the event rate at the mean of all predictors is 0.20 and where the multiple correlation of the predictor with the other predictors is 0.30, the sample size needed to detect an odds ratio of 1.75 expressed in standardized metrics is about 170 and for an odds ratio in standardized metrics of 2.00 is about 110. Our projected completed sample sizes exceed these thresholds. Thus, we should have sufficient power to evaluate Aim 2 for continuous and non-continuous outcomes.

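### Table 2 schedules every mediator at 1 month only, against five other places in the plan; if it is followed, Aim 2 has no baseline mediators and no communication trajectory

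*Combined protocol and SAP*

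**What the plan says.** Table 2 is the only construct-by-wave schedule in the plan. Under the heading "Tertiary Outcomes (Mediators" it has two rows: parent communication (parent and teen report) and "Alcohol Motives/Expectancies/Willingness/Norms" (teen report). Both carry time T2. The outcomes, for example "Alcohol Use (Daily Drinking, HED, Quantity/Frequency, Peak", carry T1-T3.

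Other parts of the plan give a different schedule:

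- Research Strategy, Objective 2, Randomized Trial Design: "Youth will complete assessments of all the variables in" Figure 1, at three times.
- Protection of Human Subjects, Sources of Material: the baseline youth survey includes "willingness to use alcohol, alcohol motives, alcohol expectancies, norms about alcohol use, parenting behaviors and basic demographics".
- Section 4.2.a (Narrative Study Description) and the Statistical Design and Power attachment: all dyads give the variables at three times.
- Participant Recruitment and Procedures: the teen follow-up surveys are meant to show change in the mediators.

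The analyses that use the mediators are in the Data Analysis section. Aim 2 relates "effects of the PN on predictors at the immediate post-PN assessment (1 mo. follow-up" to outcomes at 6 months, by structural equation modeling with a joint-significance test. The subsection on covarying trajectories would "examine the changes over time in parental communication (PCOM) associated with the changes over time in alcohol use". The Aim 2 power text names "the mediators (parent-child communication, parental monitoring, parental permissiveness" as mediators; neither Table 2 nor section 4.3 lists a measure for the last two.

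**The concern.** Randomization protects the path from arm to mediator. It does not protect the path from mediator to outcome: teens who differ in motives or norms before the trial are likely to differ in later drinking whatever their parents received. The baseline mediator is the obvious control for this, and it cannot be recovered if it is not asked at T1. Whoever programs the survey may well work from Table 2.

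Two further consequences follow if Table 2 is taken literally. A trajectory of parental communication cannot be estimated from one wave. And H5, which has communication acting on student factors, would rest on two variables measured at the same time.

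Mediation is Specific Aim 2, one of the planned publications, and part of the plan's main success benchmark.

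**Working it through.** **1. The plan's own Aim 2 figures.** The only stated numbers tied to this analysis are the sample sizes in Statistical Design and Power. Alpha is not given; 0.05 two-sided is assumed.

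- Regression: f² = 0.05/(1 − 0.25) = 0.0667. The noncentral F test of one coefficient, with λ = f²(u + v + 1), gives n = 124 with 5 predictors and 125 with 6. The plan says about 125.
- Logistic: n = (1.960 + 0.842)²/[p(1 − p)(ln OR)²(1 − R²)] with p = 0.20 and R = 0.30. OR 1.75 gives 7.849/(0.16 × 0.3132 × 0.91) = 172 against about 170. OR 2.00 gives 7.849/(0.16 × 0.4805 × 0.91) = 112 against about 110.

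The figures reproduce and are not in dispute. Neither worked example includes a baseline mediator among its predictors.

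**2. Is the communication trajectory estimable?** Take a linear parallel growth model with alcohol use at 0, 1 and 6 months, communication at w waves, arm as covariate and free residual variances.

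- Parameters: 4 latent means + 10 latent variances and covariances + 4 arm effects + (3 + w) residual variances = 21 + w.
- Moments, with k = 3 + w measures: 2k + k(k + 1)/2.

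| Communication waves | Parameters | Moments | df | Jacobian rank | Identified |
|---|---|---|---|---|---|
| T2 only (Table 2) | 22 | 18 | −4 | 15 | No |
| T1, T2 | 23 | 25 | 2 | 21 | No, without added constraints |
| T1-T3 | 24 | 33 | 9 | 24 | Yes |

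**3. What a missing baseline mediator does to the mediator-to-outcome path.** Let M0 and M1 be the mediator at T1 and T2, and Y0 and Y3 the outcome at T1 and T3, all standardized. Set the true M1-to-Y3 effect to zero. The documents give none of the values below; they are assumptions.

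*Confounding through baseline values only.* M1 = ρM0 + error; Y3 = sY0 + qM0 + error; corr(M0, Y0) = c; ρ = 0.5 to 0.7, c = 0.3 to 0.5, q = 0.1 to 0.2, s = 0.5.

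- No adjustment: b = ρ(sc + q). Lowest 0.5 × (0.15 + 0.1) = 0.125; highest 0.7 × (0.25 + 0.2) = 0.315.
- Adjusting for Y0: b = ρq(1 − c²)/(1 − ρ²c²). Lowest (ρ = 0.5, c = 0.5, q = 0.1) 0.0375/0.9375 = 0.04; highest (ρ = 0.7, c = 0.3, q = 0.2) 0.1274/0.9559 = 0.13.
- Adjusting for Y0 and M0: b = 0.

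*An unmeasured stable trait.* If one trait drives all four variables, so that every pairwise correlation is r, adjusting for Y0 gives b = r/(1 + r), and adjusting for Y0 and M0 gives b = r/(1 + 2r). For r = 0.30 these are 0.23 and 0.19; for r = 0.49 they are 0.33 and 0.25. The baseline mediator reduces the bias but does not remove it.

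**4. H5 with both variables at T2.** In one simulated data set of n = 320, the model with communication leading to the student factor and the model with the reverse direction have the same log-likelihood, −918.017. Fit cannot show direction. Section 4.3 also has communication recalled over the past six months. A report one month after baseline therefore covers about five months before it, which is a further reason to have the T1 value.

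**5. Parent report.** Randomized Trial Design and Table 1 give parents one survey, at 1 month. Parent-reported communication is single-wave whichever teen schedule applies, and that too conflicts with the statements that all dyads report three times.

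**The case against.** The strongest reply is that Table 2 is the outlier. Most of the text points to three waves, and T2 in the mediator rows may simply mark the wave at which mediators enter the Aim 2 model. On that reading baseline values exist, teen-reported communication has three waves, and only the table needs correcting. This largely stands: the defect is an unreconciled contradiction, and the harms above hold only if Table 2 governs. However, Data Collection and Measurement points to Table 2 for the assessment schedule, so the table cannot be dismissed. Nor does Aim 2 say that the baseline mediator is a covariate. The Covariates paragraph commits to controlling sources of spuriousness in general, names no such adjustment, and could not apply it to values never collected.

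Some stronger inferences are tempting but not supported:

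- *That a committed analysis is lost.* The parallel trajectory model is described as something the analyses can be extended to. The alcohol-only growth model uses T1-T3 outcomes and is unaffected.
- *That mediation has no time order.* Aim 2 already puts mediators at 1 month and outcomes at 6 months. Only the communication-to-student-factor step is simultaneous.
- *That false mediation would be declared in most trials.* High rejection rates can be produced for the mediator-to-outcome path by assuming a strong unmeasured trait, but the documents give no such correlations, and correcting Table 2 would only partly cure that bias. Joint significance also requires a significant path from PN to the mediator. If PN does not move the mediator, false mediation stays at or below about 5%.

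Parental monitoring and permissiveness may be meant by the parenting behaviors in the baseline survey. Figure 1 is not available to check, and that term is not a defined measure.

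**Conclusion.** The point holds as a contradiction that should be resolved before the surveys are programmed. Table 2 gives the mediators one wave; five other places imply baseline or repeated measurement. If Table 2 is followed, the communication trajectory is not identified (df −4, against 9 with three waves), and the mediator-to-outcome path cannot be adjusted for the baseline mediator. The resulting spurious path is about 0.04 to 0.13 under the assumed values when confounding runs only through baseline values, and baseline-mediator adjustment then removes it. With an unmeasured stable trait, that adjustment only reduces it. These sizes are illustrations, not estimates for this trial. Even if the three-wave text governs, the Aim 2 adjustment set still has to be named. These are tertiary outcomes, and no Aim 1 conclusion depends on them.

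**What to change.** 1. In Table 2, change teen-reported communication and teen motives, expectancies, willingness and norms to T1-T3. Keep parent-reported communication at T2, and correct the statements that all dyads report at three times. T1 and T2 alone would serve the adjusted mediation paths but not the growth extension.
2. In Aim 2, state that every mediator-to-outcome path adjusts for the T1 mediator and the T1 outcome.
3. For H5, adjust the T2 communication to T2 student-factor path for the T1 values of both, and report it as not time-ordered. A T2 communication to T3 student-factor test can be added as a sensitivity analysis. It would use about 280 rather than 320 teens, by the plan's retention figures. It would also put student factors at the same wave as the 6-month outcome, so with two follow-up waves both links of the chain cannot be strictly ordered.
4. Either list measures and waves for parental monitoring and permissiveness in Table 2 and section 4.3, or remove them from the Aim 2 power text.

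The cost is mainly table and analysis wording. The Randomized Trial Design text and Sources of Material already promise the teen items, so added survey burden should be small.
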